A PHASE II, OPEN LABEL, MULTI-DOSE STUDY OF ^{89}Zr -DF-IAB22M2C (CD8 PET TRACER) FOR POSITRON EMISSION TOMOGRAPHY (PET/CT) IN PATIENTS WITH SELECTED ADVANCED OR METASTATIC SOLID MALIGNANCIES WHO ARE SCHEDULED TO RECEIVE STANDARD OF CARE IMMUNOTHERAPY ONLY, AS SINGLE AGENT OR IN COMBINATION.

Protocol Number: IAB-CD8-201
Version Number: Version 3.1
Version Date 28 OCT 2020
Development Phase: Phase II
Investigational Compound: ^{89}Zr -Df-IAB22M2C (CD8 PET Tracer)
NCT Number: NCT03802123

Sponsor: ImaginAb Inc.

Name of Sponsor/Company: ImaginAb Inc. Name of Study Product: ⁸⁹ Zr-Df-IAB22M2C	
Protocol Number: IAB-CD8-201	Indication: Patients with Selected Advanced and Metastatic Solid Tumors including Melanoma, Non-Small Cell Lung Cancer, Renal Cell Carcinoma, Squamous Cell Carcinoma of the Head and Neck, Colorectal Cancer-MSI high, Triple Negative Breast, Bladder, Cervical, and Esophagogastric Cancers
Title of Study: A Phase II, Open Label, Multi-Dose Study Of ⁸⁹ Zr-Df-IAB22M2C (CD8 PET Tracer) For Positron Emission Tomography (PET/CT) In Patients With Selected Advanced Or Metastatic Solid Malignancies Who Are Scheduled To Receive Standard of Care Immunotherapy As Single Agent or In Combination.	
Study Center: Up to 20 research sites in USA, Canada, Europe and Australia	
Planned Number of Subjects: Approximately 47 Subjects	Study Development Phase: II
Objectives: Primary Objectives: 
 Evaluate safety of repeat doses of ⁸⁹Zr-Df-IAB22M2C (CD8 PET Tracer) Establish the relationship between ⁸⁹Zr-Df-IAB22M2C (CD8 PET Tracer) PET/CT lesion uptake with CD8+ cells by Immunohistochemical staining (IHC) Secondary Objective: 
 Assess ⁸⁹Zr-Df-IAB22M2C (CD8 PET Tracer) uptake at Baseline and On-treatment in tumor lesions and reference tissues, including CD8+-cell rich reference tissues Measure potential change in ⁸⁹Zr-Df-IAB22M2C (CD8 PET Tracer) uptake on PET in tumor lesions and reference tissues, including CD8+-cell rich tissues reference between baseline and On-treatment. Measure potential changes in ⁸⁹Zr-Df-IAB22M2C (CD8 PET Tracer) uptake on PET_{baseline} and PET_{Tx} scans compared to change in CD8+ cells in tumor lesions by IHC if the same lesion was biopsied at Baseline and On-Treatment visits Assess biodistribution for ⁸⁹Zr-Df-IAB22M2C (CD8 PET Tracer) on PET_{baseline} and PET_{Tx} scans. Exploratory Objectives: 
 Explore visual and quantitative ⁸⁹Zr-Df-IAB22M2C (CD8 PET Tracer) PET measurements that best correlate with CD8+ cells as determined by IHC. Estimate positive predictive value, negative predictive value, sensitivity and specificity of ⁸⁹Zr-IAB22M2C (CD8 PET Tracer) PET for detecting CD8+ cells as determined by IHC. Explore the visual and quantitative ⁸⁹Zr-Df-IAB22M2C (CD8 PET Tracer) PET measurements with clinical outcomes. Evaluate the visual and quantitative ⁸⁹Zr-Df-IAB22M2C (CD8 PET Tracer) PET measurements with RECIST 1.1 radiology responses Evaluate the correlation of ⁸⁹Zr-Df-IAB22M2C (CD8 PET Tracer) uptake with immune infiltrates and other molecular biomarkers (such as CD4, CD8, PD-1 and PD-L1) expression by IHC 	

Study Outcomes:**Primary Outcome Measure:**

- The safety and tolerability of repeat doses of ^{89}Zr -Df-IAB22M2C (CD8 PET Tracer) will be assessed by local and systemic signs and symptoms of infusion reactions, incidence of adverse events per CTCAE criteria, changes in laboratory test results, vital signs and 12-lead electrocardiogram (ECG) findings prior to and within 1 hour post injection.
- Correlation of ^{89}Zr -Df-IAB22M2C (CD8 PET Tracer) uptake in biopsied tumors as determined by SUV-based quantitative measures :SUVmax, SUVpeak, SUVmean, CD8 tumor volume (volume of tumor tissues with increased CD8 uptake with SUV > 40% SUVmax), and Tumor: Reference ratios with CD8+ cell measurements as determined by IHC from biopsy samples.

Secondary Outcome Measures:

- Assessment of Baseline and On-Treatment ^{89}Zr -Df-IAB22M2C (CD8 PET Tracer) uptake and distribution in tumors and lymphoid organs, and measurement of change between the paired observations, as determined by:
 - Tumor uptake analysis as described by visual scoring scales
 - Lymph node chain visibility defined as location and number of nodes in lymph node chains identified with elevated ^{89}Zr -Df-IAB22M2C (CD8 PET Tracer) activity.
- Assessment of Baseline and On-Treatment ^{89}Zr -Df-IAB22M2C (CD8 PET Tracer) uptake and distribution in tumors and lymphoid organs and measurement of change between the paired observations, as determined by:
 - SUV-based quantitative analysis: SUVmax, SUVpeak, SUVmean, CD8 tumor volume (volume of tumor tissues with increased CD8 uptake with SUV > 40% SUVmax), and Tumor: Reference ratios
 - Visual and SUV-based quantitative analysis (SUVmax, SUVpeak, SUVmean) in tumor and reference tissues including lymph nodes, spleen and bone marrow.
- Measurement of change in ^{89}Zr -Df-IAB22M2C (CD8 PET Tracer) uptake in biopsied tumors as determined by SUV-based quantitative analysis : SUVmax, SUVpeak, SUVmean, CD8 tumor volume (volume of tumor tissues with increase CD8 uptake with SUV > 40% SUVmax) and Tumor: Reference ratio from Baseline to On-Treatment PET scans and correlation with change in CD8+ cells as determined by IHC from biopsy samples obtained prior to and 4 to 7 weeks after the start of immunotherapy.
- Description of biodistribution patterns of ^{89}Zr -Df-IAB22M2C (CD8 PET Tracer) on PET_{baseline} and PET_{Tx} and any changes in biodistribution between baseline and On-Treatment.

Exploratory Outcome Measures:

- Correlation of visual and quantitative ^{89}Zr -Df-IAB22M2C (CD8 PET Tracer) uptake in tumor lesions with change in CD8+ cells as determined by IHC from biopsy samples obtained prior to and 4 to 7 weeks after the start of immunotherapy.
- Estimation of positive predictive value, negative predictive value, sensitivity and specificity of ^{89}Zr -IAB22M2C (CD8 PET Tracer) PET for detecting CD8+ cells as determined by IHC.
- Correlation of ^{89}Zr -Df-IAB22M2C (CD8 PET Tracer) uptake with clinical outcomes (response rates, duration of response, disease stability rate and PFS) at defined intervals as determined by the local investigator.
- Correlation of ^{89}Zr -Df-IAB22M2C (CD8 PET Tracer) uptake with radiologic responses based upon:
 - Correlation of subject response by RECIST 1.1 compared to visual and quantitative SUV-based analysis
 - Correlation of RECIST 1.1 target lesion response as determined by best change in lesion diameter while on immunotherapy compared to visual and quantitative SUV-based analysis at baseline and On-treatment PET/CT scans.
- Correlation of ^{89}Zr -Df-IAB22M2C (CD8 PET Tracer) tumor and lymph node uptake with immune infiltrates and other molecular biomarker (CD8) expression by IHC

Name of Sponsor/Company: ImaginAb Inc. Name of Study Product: ^{89}Zr -Df-IAB22M2C	
Protocol Number: IAB-CD8-201	Indication: Patients with Selected Advanced and Metastatic Solid Tumors including Melanoma, Non-Small Cell Lung Cancer, Renal Cell Carcinoma, Squamous Cell Carcinoma of the Head and Neck, Colorectal Cancer-MSI high, Triple Negative Breast, Bladder, Cervical, and Esophagogastric Cancers

 Correlation of the ^{89}Zr-Df-IAB22M2C (CD8 PET Tracer) uptake on a subset of PET_{baseline} and PET_{tx} scans that have been virtually reconstructed with lower theoretical doses of ^{89}Zr-Df-IAB22M2C (CD8 PET Tracer) with CD8+ cells from IHC analysis. 	
Safety Assessments: 
 Incidence of Treatment-Emergent Adverse Events (AEs). Incidence of withdrawals due to AEs. Change/shifts in laboratory values. Change in vital signs. Change in Electrocardiogram (ECG) parameters. Anti-Drug Antibodies Serious Adverse Events (SAEs) 	
Trial Design: 
 Eligible subjects who meet Inclusion/Exclusion criteria will receive ^{89}Zr-Df-IAB22M2C (CD8 PET Tracer) as an IV infusion within 1 week prior to the onset of immunotherapy, and 4 to 6 weeks after start of immunotherapy. Conventional CT Chest, Abdomen and Pelvis (including Neck for SCCHN subjects) or MRI or whole body ^{18}FDG-PET scan will be performed within 45 days prior to 1st infusion of ^{89}Zr-Df-IAB22M2C (CD8 PET Tracer). Fresh tumor biopsy (Preferred3 to 5 core biopsies) will be performed at: 
 Baseline: within -28 to -7 days prior to 1st infusion or 0-6 days after 1st infusion of ^{89}Zr-Df-IAB22M2C (CD8 PET Tracer) and its associated PET/CT scan of ^{89}Zr-Df-IAB22M2C (CD8 PET Tracer) at 24hrs post injection. Within 2 weeks after 2nd infusion of ^{89}Zr-Df-IAB22M2C (CD8 PET Tracer) and its associated PET/CT scan at 24 hrs post injection. Archival tumor biopsy tissues obtained within 2 months (60 days) prior to 1st infusion of ^{89}Zr-Df-IAB22M2C (CD8 PET Tracer) may be submitted in place of Baseline fresh biopsy, with approval from the Sponsor. PET/CT scans (PET_{baseline} and PET_{tx}) will be obtained at 24 \pm 3 hours after each infusion of ^{89}Zr-Df-IAB22M2C (CD8 PET Tracer). Anti-drug antibody (ADA) blood samples will be collected at the following time points: at Baseline, prior to receiving the 2nd infusion of ^{89}Zr-Df-IAB22M2C (CD8 PET Tracer), and at End-of-Study safety follow-up visit. Safety follow-up: 4-6 weeks after the last dose of ^{89}Zr-Df-IAB22M2C (CD8 PET Tracer). Extended follow-up: collect Standard of Care (SOC) imaging only, up to 12 months after start of immunotherapy. 	
The detailed study schedule and assessments in each visit are provided in Section Error! Reference source not found. of the protocol.	
Tumor Biopsy: 
 Fresh tumor biopsy from a RECIST 1.1 measurable lesion (excluding cutaneous lesions) within -28 to -7 days prior to 1st infusion immunotherapy or 1 to 6 days after 1st infusion of ^{89}Zr-Df-IAB22M2C (CD8 	

Name of Sponsor/Company: ImaginAb Inc. Name of Study Product: ^{89}Zr -Df-IAB22M2C	
Protocol Number: IAB-CD8-201	Indication: Patients with Selected Advanced and Metastatic Solid Tumors including Melanoma, Non-Small Cell Lung Cancer, Renal Cell Carcinoma, Squamous Cell Carcinoma of the Head and Neck, Colorectal Cancer-MSI high, Triple Negative Breast, Bladder, Cervical, and Esophagogastric Cancers

PET Tracer) and its associated PET/CT scan; and within 2 weeks after 2nd infusion of ^{89}Zr-Df-IAB22M2C (CD8 PET Tracer) and its associated PET/CT scan.
 
 • If biopsy will be performed after the PET/CT scan (either Baseline or On-treatment), image guided biopsy will be the preferred method, where the lesion is chosen based on CD8+ PET signal on the CD8 PET/CT scan. • The need for the Baseline biopsy will be considered on a case by case basis following discussion with the Sponsor. • If a patient has had a diagnostic biopsy within 2 months (60 days) prior to the 1st infusion of ^{89}Zr-Df-IAB22M2C (CD8 PET Tracer), the archival tissue can be submitted for IHC analysis, with approval of the Sponsor, provided the specimen is of adequate quality and the biopsy was obtained from a lesion that is RECIST 1.1 measurable and remains visible on conventional imaging with CT/MRI. If these conditions are met, then the patient can be exempt from the Baseline biopsy. • Archival tumor tissue must have been obtained after last systemic therapy. The lesion from which the archival tissue is obtained should not have received radiation post-biopsy. • For the 2nd biopsy (within 2 weeks after 2nd infusion of ^{89}Zr-Df-IAB22M2C [CD8 PET Tracer] and PET/CT scan), optional surgical resection may be performed in place of biopsy if investigator determines the tumor as resectable. • Assuming a correlation between Tumor SUVmax to SUVmean Aorta reference tissues and CD8+ cell measurements by IHC of 0.65, 47 patients will be needed to obtain a width of 0.30. The 95% confidence interval is 0.47-0.78, which would be in the range of a good correlation. 	

Name of Sponsor/Company: ImaginAb Inc. Name of Study Product: ⁸⁹ Zr-Df-IAB22M2C	
Protocol Number: IAB-CD8-201	Indication: Patients with Selected Advanced and Metastatic Solid Tumors including Melanoma, Non-Small Cell Lung Cancer, Renal Cell Carcinoma, Squamous Cell Carcinoma of the Head and Neck, Colorectal Cancer-MSI high, Triple Negative Breast, Bladder, Cervical, and Esophagogastric Cancers
Inclusion Criteria:	

Subjects will be eligible for enrollment in the study only if they meet ALL of the following criteria:
 
 1. Patients with advanced or metastatic solid tumors including Melanoma, Non-Small Cell Lung Cancer, Renal Cell Carcinoma, Squamous Cell Carcinoma of the Head and Neck, Colorectal Cancer (MSI-High) Triple Negative Breast, Bladder, Cervical and Esophagogastric cancers selected to receive standard-of-care immunotherapy only, as single agent or in combination. 2. Patients with at least one non-irradiated lesion: 
 • At least 1 non-irradiated measurable lesion documented on CT, MRI (per RECIST criteria 1.1) or are FDG-avid on FDG-PET within 45 days prior to first ⁸⁹Zr-Df-IAB22M2C (CD8 PET Tracer) infusion. • At least 1 non-cutaneous and non-bone lesion that is accessible, per investigator's assessment, and eligible for biopsy. If only a single RECIST 1.1 measurable lesion is present, investigator to determine if the tumor biopsy could interfere with RECIST 1.1 assessments of response. 3. Eastern Cooperative Oncology Group (ECOG) performance status ≤ 2. 4. Meeting all clinical safety lab values per institution's standard of care, or Investigator's discretion, for patients receiving cancer treatment. 5. Age ≥ 18 years. 6. Ability to understand the purposes and risks of the trial and has signed an IRB-approved informed consent form. 7. Willingness and ability to comply with all protocol required procedures. 8. For men and women of child-producing potential, use of effective double barrier contraceptive methods during the study, up to 30 days after the last administration of the investigational product. 	
Exclusion Criteria:	

Subjects will NOT be eligible for enrollment in the study if they meet ANY of the following criteria:
 
 1. Serious nonmalignant disease or conditions that in the opinion of the Investigator and/or ImaginAb could compromise protocol objectives. 2. Patients with a single RECIST 1.1 measurable lesion for biopsy of which, per Investigator's assessment, is likely to interfere with RECIST 1.1 assessments of response. 3. Patients who have any splenic disorders, or had splenectomy, that in the opinion of the Investigator and/or ImaginAb could compromise protocol objectives. 4. Pregnant women or nursing mothers. 5. Life expectancy < 6 months 	

Statistical Considerations:

All collected study data will be presented in subject data listings. Statistical analyses will be performed using SAS® for Windows, version 9.4 or later. Descriptive statistics (n, mean, standard deviation, median, minimum and maximum) will be presented for continuous variables. Frequencies and percentages will be presented for categorical variables.

Sample Size Determination and Rationale

The sample size calculation is based on the co-primary outcome measure of correlation of ^{89}Zr -Df-IAB22M2C (CD8 PET Tracer) uptake as determined by Tumor SUVmax to SUVmean Aorta reference tissue with CD8+ cell measurement as determined by IHC from biopsied lesions. Since there are no validated comparator studies or imaging scans that can serve as reference values scans for CD8+ cell count, the objective of this study is to estimate the correlation between CD8+ cells and quantitative uptake by PET with sufficient precision.

The objective is to estimate the Spearman's correlation coefficient with a 0.30 width (width of the 95% confidence interval calculated based on Bonett and Wright (2000) method). The sample size is adjusted for intra-patient correlation assuming two observations per patient (baseline and on-treatment) and a moderate intra-patient correlation of 0.30 (plausible as patients will receive treatment between the two observations). Assuming a correlation between Tumor SUVmax to SUVmean Aorta reference tissue and CD8+ cell measurements of 0.65, 47 patients will be needed to obtain a width of 0.30. The 95% confidence interval is 0.47-0.78, which would be in the range of a good correlation. If the estimated correlation is 0.75, the 95% confidence interval becomes 0.61-0.85 (width = 0.24). If the estimated correlation is 0.50, the 95% confidence interval becomes 0.29-0.66 (width = 0.37).

Analysis Populations

Efficacy population

The efficacy population is defined as all subjects who have received at least one dose of study imaging agent and have at least one CD8 PET scan of adequate quality and corresponding core biopsy samples of adequate quality from at least one location.

For correlating treatment-related change in PET signal with change in CD8+ cell measurements on IHC: Efficacy population is defined as all subjects who have paired Baseline and On-treatment CD8 PET scans and corresponding paired biopsy samples.

Per Protocol (PP) Population

The Per Protocol (PP) population is defined as the set of subjects who meet the efficacy population requirements and were not associated with a major protocol violation. This population will be identified before the database lock.

Safety Population

The Safety population is defined as all subjects receiving at least one dose of the study imaging agent.

Analysis Methods:

The primary analysis of the primary and secondary outcome measures will be conducted using the PP population. Analyses of safety outcomes will be conducted using safety population.

Safety Analysis:

Analyses of safety outcomes will be conducted using the safety population.

Adverse events will be coded using MedDRA. Treatment Emergent AE's (TEAE) are defined as events with an onset on or after the first treatment. TEAEs will be summarized by treatment group and by stage of the study, System Organ Class, and preferred term. The following TEAE summaries will be provided:

- TEAEs by severity grade
- TEAEs by relationship to study treatment.

Name of Sponsor/Company: ImaginAb Inc. Name of Study Product: ^{89}Zr -Df-IAB22M2C	
Protocol Number: IAB-CD8-201	Indication: Patients with Selected Advanced and Metastatic Solid Tumors including Melanoma, Non-Small Cell Lung Cancer, Renal Cell Carcinoma, Squamous Cell Carcinoma of the Head and Neck, Colorectal Cancer-MSI high, Triple Negative Breast, Bladder, Cervical, and Esophagogastric Cancers

In addition, separate summaries of serious adverse events, and adverse events resulting in discontinuation of study treatment will be presented.
 
The first co-primary objective is the evaluation of the safety of repeat doses of ^{89}Zr-Df-IAB22M2C (CD8 PET Tracer). Adverse events will be graded using CTCAEv5. All grades will be tabulated overall and by injection number (1st injection vs 2nd injection). Considering that the safety profile of one dose has been established before, no severe (grade ≥ 3) events are expected, but safety will be closely monitored and safety data will be reviewed by a data safety committee.
 
In addition, all the data from physical examination, 12-Lead ECG, Serum chemistry, hematology, and vital signs will also be descriptively summarized.
	

Efficacy Analysis:
 
The primary analysis of the primary and secondary outcome measures will be conducted using the PP population.
 
For the efficacy outcome measures, the data will be summarized and compared according to the variable type. Continuous data summaries will include:
 
 Descriptive summary of number of observations, mean, standard deviation, median, 1st and 3rd quartile and minimum and maximum values. Inferential statistics include: 
 Pearson correlations T-test or ANCOVA using the baseline value as a covariate, if the Normality assumption is met non-parametric or rank based analysis, if the Normality assumption is not met. 
Categorical data summaries will include:
 
 Frequency counts and percentages. Chi square test or Logit model for inferential statistics. 
To establish the relationship of the PET/CT uptake with CD8+ cells (the second co-primary objective), the main analysis will be the Spearman's correlation coefficient between Tumor SUVmax to Aorta reference tissue and CD8+ cells value at all times (baseline and post-treatment). The correlation will then be estimated using SUVpeak, SUVmean, CD8 tumor volume (defined as the volume of tumor tissue with SUV $> 40\%$ of SUVmax), and other tumor: reference ratio. The correlation will be given with a two-sided 95% confidence interval accounting for clustering with subjects as clusters (as most subjects will have measurements at 2 times). Those analyses will be repeated separately at baseline and post-treatment as exploratory analyses.
 
The first 15 to 20 patients might be described during the study in order to check the technical quality of the data and the imaging. This description will not allow for stopping the trial, no statistical inference will be done, and therefore no type-I error is spent at this stage.

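### The biopsy windows allow a baseline sample after the first immunotherapy dose and an on-treatment sample up to week 8, but the change outcomes need samples taken before treatment and at weeks 4 to 7

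*Combined protocol and SAP*

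**What the plan says.** All references are to the combined protocol and SAP, whose supplied text is at synopsis level.

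- **Tracer timing (Trial Design).** The two infusions are given "within 1 week prior to the onset of immunotherapy, and 4 to 6 weeks after start of immunotherapy". Each is followed by a PET/CT scan 24 ± 3 hours later.
- **Baseline biopsy.** Trial Design gives the window as "within -28 to -7 days prior to 1st infusion or 0-6 days after 1st infusion of" the tracer and its scan. Tumor Biopsy gives it as "within -28 to -7 days prior to 1st infusion immunotherapy or 1 to 6 days after 1st infusion of" the tracer and its scan. Only the post-scan option matters here, because every other permitted source of baseline tissue predates immunotherapy. The post-scan option is a planned one: "If biopsy will be performed after the PET/CT scan (either Baseline or On-treatment), image guided biopsy will be the preferred method", with the lesion chosen on its CD8 signal.
- **On-treatment biopsy.** Trial Design has "Within 2 weeks after 2nd infusion of" the tracer and its scan. Tumor Biopsy repeats the limit: "For the 2nd biopsy (within 2 weeks after 2nd infusion of" the tracer and its scan.
- **Outcomes.** The secondary outcome on change, and one exploratory outcome, use biopsies taken before immunotherapy starts and again between weeks 4 and 7 of it. The Objectives limit the secondary change comparison to lesions biopsied at both visits.
- **Populations.** The change-analysis population needs paired scans and paired biopsies and states no time limits. The Per Protocol population removes only major protocol violations.
- **Schedule.** "The detailed study schedule and assessments in each visit are provided in Section" a section that is not part of the supplied text.

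**The concern.** A site can follow the procedure windows exactly and still produce a sample that the outcome definition does not cover. Nothing in the population definitions then says what to do with it. The analyst must either use a pair that lies outside the outcome or drop a patient whose site did as instructed, and that choice should be settled before results are seen.

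The baseline half matters more. If the first biopsy follows the first immunotherapy dose, its CD8 count may already carry an early treatment effect, while the matching baseline PET was taken before treatment. The change in PET and the change in CD8 would then span different periods, and their correlation is what the secondary outcome is meant to estimate. The exploratory baseline-only correlation would have the same mismatch.

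The on-treatment half is a one-week disagreement about the end of the window. The documents show no harm from a week-8 sample as such. What is at stake is whether it counts.

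**Working it through.** **The plan's own figure.** The sample size rests on a Spearman correlation of 0.65, two observations per patient and an intra-patient correlation of 0.30. The effective n is 2 × 47 / (1 + 0.30) = 72.3. On the Fisher z scale the Bonett and Wright standard error is √[(1 + 0.65²/2) / (72.3 − 3)] = 0.132. The 95% interval is 0.475 to 0.776, width 0.301, which agrees with the stated 0.47-0.78 and 0.30. No biopsy date enters this calculation, so 47 stands.

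**Baseline biopsy.** Day 0 is the first immunotherapy dose. The tracer is given on day t, from -7 to -1. The scan comes about a day later, so a biopsy after the scan and within 6 days of the infusion falls on days t+1 to t+6.

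| Tracer day | Biopsy days | Before day 0 | On day 0 | After day 0 |
|---|---|---|---|---|
| -7 | -6 to -1 | 6 | 0 | 0 |
| -6 | -5 to 0 | 5 | 1 | 0 |
| -5 | -4 to +1 | 4 | 1 | 1 |
| -4 | -3 to +2 | 3 | 1 | 2 |
| -3 | -2 to +3 | 2 | 1 | 3 |
| -2 | -1 to +4 | 1 | 1 | 4 |
| -1 | 0 to +5 | 0 | 1 | 5 |
| Total (42) | | 21 | 6 | 15 |

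A biopsy after day 0 is possible for tracer days -5 to -1, at latest on day -1 + 6 = +5.

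Two other readings change the count but not the conclusion:
- If a tracer infusion on day 0 itself is allowed, six combinations are added, all after day 0. That gives 15 + 6 = 21 of 48, the latest on day +6.
- If the 0-6 days run from the scan, each tracer day has 7 biopsy days (t+1 to t+7). For tracer days -7 to -1 the count after day 0 is 0+1+2+3+4+5+6 = 21 of 49, the latest on day +6.

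**On-treatment biopsy.** The second tracer infusion is on day u, from 28 to 42 (15 days). The biopsy is v days later, from 1 to 14.

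- Permitted days: 28 + 1 = 29 to 42 + 14 = 56, that is, up to week 8.
- Outcome limit: 7 × 7 = day 49.
- u + v > 49 with v ≤ 14 needs u ≥ 36.
- Combinations beyond day 49: 1 for u = 36, rising by one per day to 7 for u = 42. The sum is 28 of 15 × 14 = 210 (13%).

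If the 2 weeks run from the scan, the latest day is 57.

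All these are counts of what the text permits. They are not expected rates.

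**The case against.** The strongest reply is that the baseline rule is already there. The outcome is defined on samples taken before immunotherapy, the procedure calls the biopsy a baseline biopsy, and all the windows can be met together: every tracer day from -7 to -1 leaves at least one pre-dose opportunity, if only on day 0 before dosing. On this view the procedure merely fails to repeat the rule, and the detailed schedule may well state it. Much of this stands. The outcome wording does imply the rule, and a pre-dose clause in the schedule would remove the baseline part. But sites work from the procedure windows, and the supplied ones give an explicit limit that runs past the first dose.

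A second reply is that a population definition need not repeat an outcome's time window. That is right as far as it goes. It leaves strict application of the outcome excluding samples that sites took as told.

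A third is that week 7 could mean the end of completed week 7 (day 55). Read the same way, the last infusion moves to day 48 and the last biopsy to day 62, again 7 days over.

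The affected group is also narrow, and this stands. For the secondary change objective, the baseline problem needs the same lesion biopsied at both visits, the post-scan option, a tracer infusion on day -5 or later, and a biopsy late in its window.

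A reader might go further and infer that the co-primary correlation is compromised. The documents do not support that. Under Efficacy Analysis its main analysis pools all time points, so the label baseline plays no part. The co-primary is touched only where a pre-dose PET is paired with a post-dose biopsy, and the documents give no figure for CD8 change within days of a first dose.

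**Conclusion.** The concern holds for the supplied text, at minor to moderate severity. The procedure permits a baseline biopsy up to day +5 where the outcome calls for a pre-treatment sample, and an on-treatment biopsy up to day 56 where the outcome stops at day 49. The analyses mainly affected are the secondary change correlation in same-lesion pairs, the exploratory change correlation and the exploratory baseline-only correlation.

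The 15 of 42 and 28 of 210 combinations must not be read as the share of patients affected, because the documents do not say how sites will schedule within the windows. The size and direction of any bias are unknown. It would also be wrong to infer that the outcome cannot be met, since compliant dates exist for every tracer day from -7 to -1.

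The verdict assumes that the tracer is given on days -7 to -1, that the biopsy follows the scan, and that no pre-dose rule appears in the schedule section. If one does, the baseline part falls. The week 7 versus week 8 conflict remains unless the schedule settles that too.

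**What to change.** 1. Add to the post-scan baseline option, in both Trial Design and Tumor Biopsy, that the biopsy must be taken before the first immunotherapy dose.
2. Use one on-treatment window in the procedure and in both change outcomes. Restating the outcomes as 4 to 8 weeks keeps all tissue collected under the present procedure (with the 2 weeks counted from the infusion). Shortening the biopsy window is the alternative. The clinical choice is the sponsor's.
3. In the analysis, classify each sample by its actual date relative to the first dose, so that a post-dose sample is not analysed as baseline. This needs only biopsy and first-dose dates and can be done even if sampling is complete.

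A sensitivity analysis of the co-primary without pairs of a pre-dose PET and a post-dose biopsy is optional.

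The cost is a wording amendment, one date-based derivation and some scheduling freedom. Counting day 0 before the dose as available, sites keep all 6 post-scan biopsy days for tracer days -7 and -6. For tracer days -5 to -1 they have 5, 4, 3, 2 and 1. A few samples may be lost from the change and baseline-only analyses. The sample size does not change.

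### The stated precision (width 0.30 from 47 patients) holds only if all 47 enrolled patients give two evaluable PET-biopsy pairs, and no allowance for losses is stated

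*Combined protocol and SAP*

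**What the plan says.** The synopsis sets enrolment as "Planned Number of Subjects: Approximately 47 Subjects". Under Sample Size Determination and Rationale, the aim is a Bonett-Wright 95% interval of width 0.30 for the Spearman correlation between the tumour-to-aorta uptake ratio and CD8+ cells by IHC. The calculation is described as follows: "The sample size is adjusted for intra-patient correlation assuming two observations per patient (baseline and on-treatment"), with "a moderate intra-patient correlation of 0.30 (plausible as patients will receive treatment between the two observations").

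At a correlation of 0.65 the section gives 47 patients and an interval of 0.47 to 0.78. At 0.75 it gives 0.61 to 0.85, width 0.24. For the lowest value it says: "If the estimated correlation is 0.50, the 95% confidence interval becomes 0.29-0.66 (width = 0.37"). The Tumor Biopsy section repeats the main result ("CD8+ cell measurements by IHC of 0.65, 47 patients will be needed to obtain a width of 0.30") without the two-observation assumption.

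Four other statements bear on how many pairs will be available:

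- Efficacy patients must "have at least one CD8 PET scan of adequate quality and corresponding core biopsy samples of adequate quality from at least one location", so one PET-biopsy pair is enough.
- The primary analysis uses the Per Protocol (PP) population, which removes major protocol violators from the efficacy population.
- The Efficacy Analysis section justifies clustering by subject on the ground that most patients will be measured at both times.
- The Tumor Biopsy section leaves the need for a baseline biopsy to case-by-case discussion. It also gives two routes that can save a pair. At baseline, "the archival tissue can be submitted for IHC analysis, with approval of the Sponsor". For the second specimen, "optional surgical resection may be performed in place of biopsy if investigator determines the tumor as resectable".

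**The concern.** The number needed and the number to be enrolled are the same, 47. The number needed is worked out with two evaluable pairs from every patient, but the analysis sections foresee patients with one pair and patients excluded from the PP set. No section of the supplied text says that the 47 are evaluable PP patients, gives an allowance for losses, or says what width to expect if pairs are missing.

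This matters because precision is the only justification given for the sample size. There is no hypothesis test and no power calculation. A reader will take 0.30, 0.24 and 0.37 as what about 47 enrolled patients should deliver, when they are what 94 evaluable pairs would deliver. What is at stake is an accurate statement of expected precision, not the validity of the estimate.

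**Working it through.** **Inputs from the plan.** Two-sided 95% interval (z = 1.96); Bonett-Wright method; 47 patients; two observations each; intra-patient correlation (ICC) 0.30; correlations 0.65, 0.75 and 0.50.

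**Formulas.** Effective observations: n_eff = 2·n2/(1 + ICC) + n1, where n2 patients have two pairs and n1 have one. With n1 = 0 this is the usual design-effect adjustment; the term for single-pair patients is an approximation. Standard error on the Fisher z scale: SE = √[(1 + r²/2)/(n_eff − 3)]. Limits: tanh(atanh r ± 1.96·SE).

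**Reproducing the plan.** n_eff = 2 × 47/1.30 = 72.31. At r = 0.65, SE = √(1.21125/69.31) = 0.1322 and atanh(0.65) = 0.7753. The limits are tanh(0.7753 ± 0.2591) = 0.475 and 0.776.

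| r | Computed interval | Computed width | Stated width |
|---|---|---|---|
| 0.65 | 0.475–0.776 | 0.301 | 0.30 |
| 0.75 | 0.609–0.845 | 0.237 | 0.24 |
| 0.50 | 0.291–0.664 | 0.373 | 0.37 |

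All three agree after rounding. The alternatives do not: at r = 0.65, one pair from each of 47 patients gives 0.379, and 94 independent pairs give 0.262. So the stated widths come from 94 pairs with a design effect of 1.30.

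**Slack before the printed width changes.**

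| r (stated width) | Whole patients lost | Second pairs lost |
|---|---|---|
| 0.65 (0.30) | 1 → 0.3043; 2 → 0.3079 | 3 → 0.3045; 4 → 0.3057 |
| 0.75 (0.24) | 2 → 0.2424; 3 → 0.2454 | 8 → 0.2448; 9 → 0.2459 |
| 0.50 (0.37) | 1 → 0.3767 | 1 → 0.3740; 2 → 0.3754 |

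**Illustrative losses.** The documents give no rates, so these are assumptions: (a) no patient lost, 80% with two pairs; (b) 10% lost, 80% of the rest with two pairs; (c) 20% lost, 70% of the rest with two pairs. For example, (b) leaves 42.3 patients, 33.84 with two pairs and 8.46 with one, so n_eff = 2 × 33.84/1.30 + 8.46 = 60.52.

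| Scenario | n_eff | Width, r = 0.65 | Width, r = 0.75 | Width, r = 0.50 |
|---|---|---|---|---|
| Complete | 72.31 | 0.301 | 0.237 | 0.373 |
| (a) | 67.25 | 0.313 | 0.246 | 0.387 |
| (b) | 60.52 | 0.331 | 0.261 | 0.409 |
| (c) | 51.77 | 0.359 | 0.284 | 0.443 |

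At r = 0.65 the ratios to complete data are 0.313/0.301 = 1.04, 0.331/0.301 = 1.10 and 0.359/0.301 = 1.19.

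**Sensitivity at r = 0.65.**

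| Assumption | Complete | (a) | (b) | (c) |
|---|---|---|---|---|
| ICC 0.10 | 0.276 | 0.290 | 0.306 | 0.335 |
| ICC 0.50 | 0.325 | 0.334 | 0.353 | 0.382 |
| 0.30 read as the within-patient correlation of each measurement | 0.263 | 0.276 | 0.292 | 0.315 |

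The last row comes from simulation (bivariate normal, 40,000 runs; patients/paired 47/47, 47/38, 42/34 and 38/27). The absolute widths depend on these choices. The relative widening is stable across all of them: about 3–5% in (a), 9–11% in (b) and 17–22% in (c).

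**The case against.** The strongest reply is that this is largely disclosed and small. The two-observation assumption stands beside the sample size, and the clustered interval will reflect whatever data are obtained. Under (a) the interval at r = 0.65 still prints as 0.47 to 0.78. Some of the slack figures only mark where the second decimal changes. All of that stands, and it is why the point is minor.

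The 1.30 design effect may also be conservative. If 0.30 is the within-patient correlation of each measurement, the 0.30 target is still met under (a) and (b) (0.276 and 0.292). The plan does not state that reading, however, and its own intervals are reproduced by the 1.30 adjustment. The relative widening appears on either reading.

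Biopsies from more than one location could add observations and offset some losses. The calculation does not count on them. Archival tissue and resection can save pairs, but neither guarantees two per patient.

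Finally, a replacement rule may exist in a part of the protocol not supplied. If it replaces non-evaluable patients, much of the point falls away, and a cross-reference would then be enough.

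**Conclusion.** The concern holds, as a minor point of disclosure. The formula and the figure of 47 are correct. The widths of 0.30, 0.24 and 0.37 are complete-data values that need 94 evaluable pairs from 47 PP patients, while enrolment is also about 47 and the analysis sections do not expect every patient to supply two pairs.

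A few lost pairs change little. Under the assumed losses the width at r = 0.65 would be about 0.31 to 0.36. Those figures rest on the plan's Bonett-Wright method with a 1.30 design effect, the approximation for single-pair patients, one biopsied lesion per visit, and loss rates that the documents do not give. The consequence is a somewhat wider interval than stated; neither bias nor a test result is involved.

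**What to change.** In Sample Size Determination and Rationale, and in the repeat under Tumor Biopsy, state that 47 patients and widths of 0.30, 0.24 and 0.37 refer to 47 evaluable PP patients with two evaluable pairs each (94 pairs), with no allowance for losses. If a replacement rule exists elsewhere in the protocol, cite it there.

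Add the widths expected from about 47 enrolled patients at the sponsor's own assumed pair yield. Say that they depend on the assumed intra-patient correlation, the design-effect method and the number of biopsied lesions per patient. The widths worked out above are illustrations and should not be copied in as the sponsor's figures.

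The cost is one or two sentences in each place and a slightly less favourable stated precision. No patients are added, and the analysis and populations do not change.
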